The endpoints for this objective will assess changes in patient's clinical assessments (e.g., laboratory assessments, vital signs) between the index date and key time-points following the index date (Table 6-1). The change in clinical assessments will be summarized as the number (%) of patients experiencing a change in each clinical assessment. Changes in clinical assessments from the index date will also be presented as shift tables. Growth and development information will also be summarized for patients who were aged <18 years at the time of first dose and until the age of 18 years.

Endpoints related to objective #10: Type, frequency, seriousness, and severity per CTCAE v4.03 criteria and causality assessments of treatment-emergent adverse events

The endpoint will report adverse events defined as the appearance of (or worsening of any pre-existing) undesirable sign(s), symptom(s), or medical condition(s) that occur during the study period. As much as possible, each adverse event will be evaluated to determine:

1. Toxicity grade
2. Duration
3. Relationship to the study treatment (i.e., not related, related, unknown)
4. Whether it is serious as per medical chart (seriousness and seriousness criteria established during the MAP)
5. Action taken with respect to study treatment (i.e. dose increased; dose not changed; dose reduced; drug interrupted; drug withdrawn)
6. If a concomitant medication or additional therapy was provided (for example diet for impaired glycemic control)
7. Outcome (i.e., not recovered/not resolved, recovered/resolved, recovering/resolving, recovered/resolved with sequelae, fatal, unknown)

Adverse events will be summarized as: the number (%) of patients experiencing each adverse event, (the number (%)) of patients experiencing any CTCAE grade 3 or higher adverse event, the number (%) of patients with serious adverse events, the number (%) of events related to treatment, the number (%) of patients who received a concomitant or an additional treatment

due to adverse event. For adverse events requiring dose interruption, the duration of interruption will be reported.

Adverse events will be coded using the Medical dictionary for regulatory activities (MedDRA) terminology. The latest available MedDRA version at the time of the analyses will be used.

The outcome of adverse events will be presented as the number (%) of patients with each outcome after any event (e.g., number [%] of patients that did not recover from any event).

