Height/weight SDS and velocity SDS will be summarized using descriptive statistics (mean, standard deviation, range) for each time window, as well as by presenting number of patients with SDS values lower/higher than 5th/95th percentiles respectively. Box plots will also be plotted for key time points.

Endpoint #10: Type, frequency, seriousness, and severity criteria and causality assessments of treatment-emergent adverse events.

Adverse events summary tables will report only on-treatment assessments/events (more details in [Appendix](#)). An on-treatment adverse event is defined as any adverse event reported in the following time interval (including the lower and upper limits):

- date of first administration of study treatment; date of last administration of study treatment + 30 days or cut-off date whichever occurs first

The endpoint will report adverse events defined as the appearance of (or worsening of any pre-existing) undesirable sign(s), symptom(s), or medical condition(s) that occur during the study period. The full population will be used for reporting Adverse Events (AE) and all safety endpoints. As much as possible, each AE will be evaluated to determine:

- Toxicity grade
- Impact (“Low”, “Medium” and “High”)
- Duration
- Relationship to the study treatment (i.e., not related, related, unknown)
- Whether it is serious as per medical chart
- Action taken with respect to study treatment (i.e. dose increased; dose not changed; dose reduced; drug interrupted; drug withdrawn). If a concomitant medication or additional therapy was provided (for example diet for impaired glycemic control)
- Outcome (i.e., not recovered/not resolved, recovered/resolved, recovering/resolving, recovered/resolved with sequelae, fatal, unknown)

All AEs collected in the AE eCRF page will be listed along with the information collected on those AEs e.g. AE relationship to study drug, AE outcome etc.

AEs will be summarized by number and percentage of patients having at least one AE in each primary system organ class (SOC) and for each preferred term (PT) using MedDRA coding. A patient with multiple occurrences of an AE will be counted only once in the respective AE category. A patient with multiple CTCAE grades (version v4.03) for the same preferred term will be summarized under the maximum CTCAE grade recorded for the event. AE with missing CTCAE grade will be included in the ‘All grades’ column of the summary tables.

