CTC grading of AE may be missing for a proportion of AE as information was not collected and retrospective assignment of a grade may not be feasible precluding a comprehensive assessment of the safety profile.

A proxy variable called “impact” will be derived using all available information on each AE/medical condition and will integrate the Important Medical Event Terms (IME) list.

The EudraVigilance Expert Working Group (EV-EWG) coordinated the development of an Important Medical Event Terms (IME) list. This IME list is used by the EMA and other European regulators to facilitate the classification of suspected adverse reactions.

The list identifies MedDRA Preferred Terms (PTs) and the criteria for selection were based on the official ICH definition of seriousness.

“High” impact is defined as satisfying one of the following conditions:

- Reported as \geq Grade 3 (regardless of seriousness)
- Or reported as serious (regardless of grading)
- Or leading to dose discontinuation (regardless of grading)
- Or MedDRA Preferred Terms (PTs) reported in the IME list.

“Medium” impact is defined as an event that does not belong to “High” and satisfies one of the following conditions:

- Reported as Grade 2 (not serious)
- Or reported with a grade missing but leading to take concomitant medication and/or to alpelisib dose reduction/interruption

“Low” impact is defined as an event that does not belong to “High” or “Medium” and satisfies one of the following conditions:

- Reported as Grade 1
- Or reported with a grade missing and no action taken (i.e., no need for concomitant medications and no alpelisib dose reductions/interruption).

If an event cannot be classified into any of the above categories then it will be considered as having impact unknown.

Impact will be reported for all AEs and for medical conditions.

In AE summaries, the primary system organ class will be presented alphabetically and the preferred terms will be sorted within primary SOC in descending frequency.

The following adverse event summaries will be produced: overview of adverse events and deaths, AEs by SOC and PT, summarized by relationship (all AEs and AEs judged to be related to alpelisib), seriousness (SAEs and non-SAEs), leading to treatment discontinuation, leading to dose interruption/adjustment, including the duration of interruption, requiring a concomitant medication or an additional treatment.

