The AE will be reported overall and by age categories, differentiating between pediatric and adult population as appropriate.

Analysis of AESIs

Specific groupings of Adverse Events of Special Interest (AESI) will be considered and the number of patients with at least one event in each grouping will be reported. Such groups consist of AEs for which there is a specific clinical interest in connection with alpelisib treatment (i.e. where alpelisib may influence a common mechanism of action responsible for triggering them) or AEs which are similar in nature (although not identical). The groups are defined according to the MedDRA terms defined in the program Case Retrieval Strategy (CRS) document and will be summarized. The latest version of the CRS document available at the time of the analyses will be used.

All AESI groupings are defined through the use of Preferred Terms (PT), High Level Terms (HLT) or System Organ Classes (SOC) or through a combination of these three components.

An Excel file with the exact composition of the AEs groupings is to be used to map reported AEs to the AESI groupings. This file is an output from electronic Case retrieval Strategy (eCRS), which may be updated (i.e. it is a living document) based on review of accumulating trial data. Note that certain AEs may be reported within multiple groupings. Final deliverables will be aligned with the final eCRS version. A listing of all grouping levels down to the MedDRA preferred terms used to define each AESI will be generated.

Table 3-8 List of all AESI grouping levels and related MedDRA terms

AESI groupings	MedDRA Term
Stomatitis	Stomatitis and ulceration (HLT)
Severe cutaneous reactions (AESI)	Severe cutaneous adverse reactions (SMQ)
Rash (AESI)	Rash [BYL719] (CMQ)
Pneumonitis (AESI)	Interstitial lung disease (SMQ)
Pancreatitis (AESI)	Acute pancreatitis (excl non-specific symptoms) [STANDARD] (NMQ)
Hypersensitivity and anaphylactic reaction (AESI)	Hypersensitivity [BYL719] (CMQ)
Hyperglycaemia (AESI)	Hyperglycaemia/new onset diabetes mellitus (SMQ)
GI toxicity Nausea Vomiting Diarrhea (AESI)	Nausea, vomiting, diarrhoea (Clinical) [BYL719] (CMQ)

Analysis for AESI will be conducted as follows:

- The number (%) of patients with AESI will be reported by AESI grouping, maximum CTCAE grade and by age group.
- Action taken and outcome of each AESI
- All AEs of special interest will be listed.
- Impact.

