4.4 Laboratory parameters derivations

Grade categorization of lab values will be assigned programmatically as per NCI Common Terminology Criteria for Adverse Events (CTCAE) version v4.03. The calculation of CTCAE grades will be based on the observed laboratory values only, clinical assessments will not be taken into account. The criteria to assign CTCAE grades are given in Novartis internal criteria for CTCAE grading of laboratory parameters. The latest available version of the document based on the underlying CTCAE version v4.03 at the time of analysis will be used. For laboratory tests where grades are not defined by CTCAE v4.03, results will be graded by the low/normal/high (or other project-specific ranges, if more suitable) classifications based on laboratory normal ranges.

A severity grade of 0 will be assigned for all non-missing lab values not graded as 1 or higher. Grade 5 will not be used. For laboratory tests that are graded for both low and high values, summaries will be done separately and labelled by direction, e.g., sodium will be summarized as hyponatremia and hypernatremia.

Imputation Rules

CTC grading for blood differentials is based on absolute values. However, this data may not be reported as absolute counts but rather as percentage of WBC.

If laboratory values are provided as '<X' (i.e. below limit of detection) or '>X', prior to conversion of laboratory values to SI unit, these numeric values are set to X.

The following rules will be applied to derive the WBC differential counts when only percentages are available for a xxx differential

$$\text{xxx count} = (\text{WBC count}) * (\text{xxx \%value} / 100)$$

Further derivation of laboratory parameters might be required for CTCAE grading. For instance, corrected calcium can be derived using the reported total calcium value and albumin at the same assessment using the following formula:

$$\text{Corrected Calcium (mg/dL)} = \text{Calcium (mg/dL)} - 0.8 [\text{Albumin (g/dL)} - 4]$$

In order to apply the above formula, albumin values in g/L will be converted to g/dL by multiplying by 0.1, calcium values in mmol/L will be converted to mg/dL by dividing by 0.2495. For calculation of laboratory CTC grades 0 and 1, the normal range for derived corrected calcium is set to the same limits (in mg/dL) as for calcium.

CTC grades for the derived absolute WBC differential counts (neutrophils, lymphocytes) and corrected calcium will be assigned as described above for grading

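### Adverse events with no CTCAE grade cannot enter the grade 3 or higher count, so that percentage is a lower bound and needs a grade-missing column and an upper bound beside it

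*SAP*

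**What the plan says.** - **Ungraded events.** SAP 3.6, Endpoint #10: "AE with missing CTCAE grade will be included in the" 'All grades' column. No grade-missing column and no bound are specified.
- **Repeats of a term.** In the same section, a patient with several grades for one preferred term "will be summarized under the maximum CTCAE grade recorded for the event".
- **Denominator.** "The full population will be used for reporting Adverse Events (AE) and all safety endpoints".
- **Missingness is expected.** "CTC grading of AE may be missing for a proportion of AE as information was not collected". The SAP adds that grading after the fact may not be feasible, and that this limits the safety assessment.
- **Statistics that depend on grade.** Protocol 6.8.2 (objective #10) asks for the number and percentage "of patients experiencing any CTCAE grade 3 or higher adverse event". For AESIs, SAP 3.6 states: "The number (%) of patients with AESI will be reported by AESI grouping, maximum CTCAE grade and by age group".
- **The proxy.** SAP 3.6 derives an impact variable (High, Medium, Low, otherwise unknown) for all adverse events.
- **Laboratory grades.** SAP 4.4: "Grade categorization of lab values will be assigned programmatically" under CTCAE v4.03. These feed the laboratory tables and the hyperglycaemia time-to-onset analysis. No text connects them to adverse events recorded without a grade.

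**The concern.** Severity is part of endpoint 10, and Protocol section 9 intends the results as primary data for health authorities. The grade 3 or higher percentage is the severity figure most readers will take from the safety tables. If a patient's only severe event has no grade in the chart, that patient counts in the denominator and can never count in the numerator. The error runs in one direction only, towards a lower rate of severe events. The planned tables would not state how many patients are affected. For missing response on the primary endpoint, by contrast, SAP 3.5.3 (Sensitivity Analysis 2) already gives best-case and worst-case figures.

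**Working it through.** **Inputs**
- N = 50, the number used for precision in Protocol 6.6; about 65 eligible patients are expected (same section).
- x = patients with at least one recorded grade 3 or higher event. Not given; 5 is assumed for illustration.
- m = patients with no recorded grade 3 or higher event but at least one ungraded event. Not given; about 10%, 20% and 30% of N are assumed.

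**Plan's own figures.** The documents give no adverse event rate to reproduce. The only precision figures are in Protocol Table 6-2. Clopper-Pearson intervals at N = 50 match all four rows: 20% gives 0.100 to 0.337, 30% gives 0.179 to 0.446, 40% gives 0.264 to 0.548, and 50% gives 0.355 to 0.645.

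**Step 1: what the rule does to one patient**
- Only event is ungraded: counted in 'All grades', in no grade column, and in the denominator.
- One grade 1 record and one ungraded repeat of the same term: shown as grade 1; the ungraded occurrence disappears from the table.
- Any recorded grade 3 or higher event: counted correctly in the patient-level figure.

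So missing grades can only lower the reported percentage.

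**Step 2: bounds**

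Lower bound = x/N (the figure as planned). Upper bound = (x + m)/N. Width = m/N.

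Each such patient adds 1/50 = 2.0 percentage points, or 1/65 = 1.5 points.

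| N | x | Lower bound | m | Upper bound |
|---|---|---|---|---|
| 50 | 5 | 5/50 = 10.0% | 5 | 10/50 = 20.0% |
| 50 | 5 | 10.0% | 10 | 15/50 = 30.0% |
| 50 | 5 | 10.0% | 15 | 20/50 = 40.0% |
| 65 | 5 | 5/65 = 7.7% | 6 | 11/65 = 16.9% |
| 65 | 5 | 7.7% | 13 | 18/65 = 27.7% |
| 65 | 5 | 7.7% | 20 | 25/65 = 38.5% |

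A confidence interval does not cover this. For 5/50 the exact 95% interval is 3.3% to 21.8%, and the upper bound with m = 10 (30.0%) lies outside it.

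**Step 3: does the impact variable recover the rate?** An ungraded event is High if it is serious, led to discontinuation of treatment, or is on the Important Medical Event list. If none of these applies, it is Medium when it led to concomitant medication or to a dose reduction or interruption, and Low when no action was taken. High also takes in serious events, discontinuations and listed terms below grade 3. The listed rules use no laboratory grade. High is therefore neither a count of grade 3 or higher events nor a bound on it.

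**Step 4: would laboratory grades close the gap?** Take N = 50, x = 5, m = 10. Let L be the share of the m patients who can be resolved from laboratory values, and q the share of those at grade 3 or higher (both assumed).
- Rate = (5 + 10·L·q)/50. It runs from 10.2% (L = 10%, q = 10%) to 17.0% (L = 70%, q = 50%).
- Remaining upper bound = (5 + 10·L·q + 10·(1 − L))/50. It runs from 17.4% (L = 70%, q = 10%) to 29.0% (L = 10%, q = 50%).

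Laboratory grades narrow the range under these assumptions but do not close it.

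**The case against.** The SAP does not hide the problem. It states the limitation, all safety analyses are descriptive, and the impact variable is a prespecified response that catches the ungraded events most likely to matter. All adverse events and AESIs are listed. If every grade is tabulated, subtracting the graded counts from 'All grades' shows patients with only ungraded events. Bounds on the primary endpoint create no duty to bound a safety table, and the upper bound counts even untreated ungraded events as severe.

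Much of this stands, and it keeps the point modest. Subtraction, however, misses an ungraded repeat behind a recorded grade 1, and a listing is not a summary. A missing column and a range also do not conflict with the SAP's rule against imputing secondary endpoints, because they impute nothing.

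A reader might infer three stronger things that the documents do not support:
- *That the SAP classes ungraded events as below grade 3.* It assigns them no grade; the lower bound follows from the arithmetic of the percentage.
- *That many ungraded events could be graded from laboratory values.* Protocol 6.8.2 says laboratory findings are captured as adverse event terms, but no share is given. Of the eight AESI groupings, only hyperglycaemia has a stated analysis based on laboratory grades. Laboratory severity is not lost either: worst grades and shift tables are reported under objective #9.
- *That laboratory grades should be filled into the main tables.* SAP Table 4-2 sets missing end dates, including those of ongoing events, to the end of the study period, and Table 4-1 sets some partial start dates to treatment start. An ungraded event could then inherit an unrelated laboratory peak. SAP 4.4 also bases these grades on observed values alone, without clinical assessment.

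**Conclusion.** The concern holds in this form: whenever grades are missing, the patient-level grade 3 or higher percentage and the AESI table by maximum grade are lower bounds, and the plan gives the reader no upper bound. The impact variable is a partial remedy, not a substitute. The width is m/N, or 2 percentage points per affected patient at N = 50. How many patients are affected is not known, and the percentages above are illustrations. The conclusion rests on reading the 'All grades' rule as placing ungraded events in that column and no other. The SAP does not say 'only', but it gives no other place for them. This is a low-cost reporting improvement; it does not show that the safety conclusions would be wrong.

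**What to change.** In SAP 3.6, Endpoint #10:

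1. Add a grade-missing column to the adverse event and AESI tables by grade. It should count patients with any ungraded occurrence of the term, including those who also have a graded one.
2. Report the patient-level grade 3 or higher percentage twice: with ungraded events taken as below grade 3 (lower bound) and as grade 3 or higher (upper bound). Name the table that carries it, since the SAP's list of adverse event summaries does not name one for this protocol statistic.
3. Optionally, add a separate sensitivity row that assigns the programmatic laboratory grade to ungraded laboratory-type events such as hyperglycaemia. Limit it to events with complete, non-imputed start and end dates, and keep it out of the main adverse event, AESI and impact tables.

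Cost: one column, one extra row and slightly more table programming. The downside is an upper figure that looks less favourable and is a limit, not an estimate; a footnote should say so.

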3.6.1 Statistical methods for the secondary endpoints

The secondary analyses for this study will be descriptive in nature and therefore no hypothesis testing will be performed. Descriptive analyses will be conducted where continuous data will be summarized by measures that will include the N, mean, median, standard deviation, Q1, Q3, minimum and maximum. Categorical and binary data will be presented by frequency counts and percentages.

3.6.2 Handling of missing data for the secondary endpoints

To report of the secondary endpoint all available data at that specific time point will be used. At each time point the total number of patients with available data will be shown. No imputation methods will be performed. If at the time point a parameter is missing for that patient it will not be reported.

[REDACTED]

4 Appendix

4.1 General definitions

Study treatment

The term study treatment or study drug will be used in this document and will refer to alpelisib.

Date of first administration of study drug

The date of first administration of alpelisib is defined as the first date when a non-zero dose of alpelisib is administered and recorded in the (e)CRF. This date is referred to as index date and used as reference start date.

Date of last administration of study drug

The date of last administration of alpelisib is defined as is the last date when a nonzero dose of alpelisib is administered and recorded in the (e)CRF.

Study day

The study day, describes the day of the event or assessment date, relative to the reference start date. The study day is defined as:

- The date of the event (visit date, onset date of an event, assessment date etc.) – reference start date + 1 if event is on or after the reference start date;
- The date of the event (visit date, onset date of an event, assessment date etc.) – reference start date if event precedes the reference start date.

Time unit

A year length is defined as 365.25 days. A month length is 30.4375 days (365.25/12). If duration is reported in months, duration in days will be divided by 30.4375. If duration is reported in years, duration in days will be divided by 365.25.

Baseline

For safety and efficacy evaluations, the last available assessment on or before the date of start of alpelisib is defined as “baseline” assessment.

On-treatment assessment/event and observation periods

For adverse event reporting the overall observation period will be divided into two mutually exclusive segments:

1. *pre-index date/pre-treatment period*: from up to 24 weeks prior to the index date through to the day prior to the index date.
2. *post-index date/on-treatment period*: from date of first administration of study treatment to 30 days after date of last administration of alpelisib (including start and stop date).

Safety summaries (tables, figures) include only data from the on-treatment period with the exception of baseline data which will also be summarized where appropriate (e.g. change from baseline summaries).

